7.3.2. Adverse Event Eliciting/Reporting

During the AE reporting period, study site personnel will actively seek information from each subject at each visit to document any AEs occurring since the previous visit. All AEs will be documented in response to a general question about the subject's well-being and any possible changes from the Baseline or previous visit. There will be no directed questioning for any specific AE. This does not deter the site from collecting and recording any AEs reported by the subject to site personnel at any other time.

If a potential AE is reported or observed during a Duchenne Video Assessment video after the first infusion of pamrevlumab or placebo, the DVA vendor study staff will report the potential AE to the site.

Whenever possible, diagnoses should be recorded when signs and symptoms are due to a common etiology, as determined by qualified medical study staff. The investigator is responsible for reviewing laboratory test results and determining whether an abnormal value in an individual study subject represents a clinically significant change from the subject's baseline values. In general, abnormal laboratory findings without clinical significance (based on the investigator's judgment) are not to be recorded as adverse events. However, laboratory value changes that

require treatment or adjustment in current therapy are considered adverse events. Where applicable, clinical sequelae (not the laboratory abnormality) are to be recorded as the adverse event. The investigator is expected to follow reported adverse events until stabilization or reversibility. The following attributes must be assigned to each AE:

- Description (Investigator's verbatim term describing the event)
- Dates of onset and resolution
- Severity
- Relationship to study drug
- Outcome
- Action taken regarding study drug
- Other treatment required
- Determination of "seriousness"

7.3.3. Assessing Adverse Event Severity

AEs, including abnormal clinical laboratory values, should be graded using the most current National Cancer Institute (NCI) Common Terminology Criteria for AE (CTCAE v. 5.0) guidelines. For terms not specified as part of NCI CTCAE, the following guidelines should be used to determine grade:

All AEs will be assessed for severity using the following criteria:

Grade 1, Mild: Asymptomatic or mild symptoms which the subject finds easily tolerated. The event is of little concern to the subject and/or of little-or-no clinical significance; intervention not indicated.

Grade 2, Moderate: The subject has enough discomfort to cause interference with or change in some of their age-appropriate instrumental activities of daily living (e.g., preparing meals, shopping for groceries or clothes, using the telephone, managing money); local or noninvasive intervention indicated.

Grade 3, Severe: The subject is incapacitated and unable to work or participate in many or all usual activities. The event is of definite concern to the subject and/or poses substantial risk to the subject's health or well-being; likely to require medical intervention and/or close follow-up, including but not limited to hospitalization or prolongation of hospitalization.

Grade 4, Life-threatening: The subject was at immediate risk of death from the event as it occurred.

Grade 5, Death: Fatal AE.

7.3.4. Assessing the Adverse Event's Relationship to IP

Most of the information about the safety of a drug prior to marketing comes from clinical trials; therefore, AE reports from investigators are critically important. The assessment of whether an AE is causally related to the study drug(s) using an evidence-based approach is critical in order to appropriately describe the safety profile of the study drug(s). Default reporting of individual

events as possibly related is uninformative and does not meaningfully contribute to the development of the study drug's safety profile.

The investigator must provide an evidence-based assessment of the relationship of the AE to study drug in accordance with the guidance below. Absence of an alternative cause would not normally be considered sufficient evidence to assess an event as related to study drug.

- Related:
 - Any event for which there is sufficient evidence to suggest that the study drug may have caused the event. For example, an unanticipated medical condition occurs which resolves with study drug interruption and re-occurs with re-administration of study drug; another example is a typical drug-related medical condition such as a rash that occurred shortly after first dose of study drug.
- Not Related:
 - The event represents a pre-existing underlying disease that has not worsened on study
 - The event has the same characteristics of a known side-effect associated with a co-medication
 - The event is an anticipated medical condition of anticipated severity for the study population
 - The most plausible explanation for the event is a factor that is independent of exposure to study drug

7.3.5. Reporting Serious Adverse Events (SAEs)

The investigator is responsible for ensuring that all SAEs observed by the investigator or reported by the subject that occur after signing of the informed consent/assent through 60 days after the last dose of pamrevlumab are recorded in the subject's medical record and are submitted to the Sponsor. All SAEs must be submitted to the Sponsor within 24 hours following the investigator's knowledge of the event via the SAE report form. Additionally, pamrevlumab related SAEs (including deaths) that occur after the EOS/safety follow-up visit will be reported.

If a subject is permanently withdrawn from protocol required therapies because of a serious adverse event, this information must be submitted to the Sponsor. The Sponsor will report serious adverse events and/or suspected unexpected serious adverse reactions (SUSARs) as required to regulatory authorities, investigators/institutions, and central IRBs/IECs in compliance with all reporting requirements according to local regulations and Good Clinical Practice (GCP).

There is no requirement to monitor study subjects for serious adverse events following the protocol-required reporting period or after end of study. However, these serious adverse events can be reported to the Sponsor. In some countries (e.g. European Union [EU] member states), investigators are required to report SAEs that they become aware of after end of study. If SAEs are reported, the investigator is to report them to the Sponsor within 24 hours following the investigator's knowledge of the event. SAEs reported outside of the protocol-required reporting period will be captured within the safety database as clinical trial cases for the purposes of expedited reporting; these cases will not be included in the clinical study report.

To report an SAE, the investigator must complete an SAE Report Form and fax or email the completed form to the Sponsor or its designated safety management vendor.

Full details of the SAE should also be recorded on the medical records and in EDC. The following minimum information is required:

- Subject number, sex and age
- The date of report
- A description of the SAE (event, seriousness of the event)
- Causal relationship to the study drug

Follow-up information for the event should be sent promptly.

For each SAE observed, the investigator should obtain all of the information available about the event, including (but not limited to): hospital discharge diagnoses, hospital discharge note, death certificate, appropriate laboratory findings (including autopsies and biopsy results), and clinical examinations (including radiological examinations and clinical consultations).

7.3.5.1. Reporting Serious Adverse Events to the Institutional Review Board / Independent Ethics Committee

The investigator is responsible for notifying his/her Institutional Review Board (IRB) or Ethics Committee (EC) of SAEs in accordance with local regulations. The Sponsor, or its designated safety vendor, will provide a copy of expedited safety reports to the investigator that it intends to submit to global regulatory authorities.

7.3.5.2. Deaths

The investigator will report the fatal event to the Sponsor's medical monitor. The investigator must provide a causal assessment of the relationship of the event to the study drug according to the guidance in [Section 7.3.4](#).

If the death occurred within the AE collection and reporting period (signed ICF to 60 days after last dose) and meets the reporting criteria, the investigator must submit the SAE Report Form in the same manner as described above in [Section 7.3.5](#). If the investigator becomes aware of a death occurring after the AE reporting period and considers it related to pamrevlumab, it will be reported as an SAE.

7.3.6. Pregnancies: Reporting and Follow-up of Female Partners of Subjects

The outcome of all pregnancies for female partners of male subjects should be followed up and documented as described. If a female partner of a male subject becomes pregnant while the subject is receiving study treatment or within 12 weeks after the last dose of study treatment, a Pregnancy Report Form must be completed and submitted to the Sponsor or designated safety management vendor within 24 hours of the investigator becoming aware of the pregnancy. The investigator must follow-up to completion of the pregnancy to ascertain its outcome (e.g., spontaneous miscarriage, elective termination, ectopic pregnancy, normal birth or congenital abnormality) and whether any AEs occur during the pregnancy or birth. The outcome of the pregnancy must be reported by the investigator on a Pregnancy Outcome Report Form, which

should be sent to the Sponsor and/or its designated safety vendor within 24 hours of the investigator becoming aware of the outcome.

Pregnancy itself is not an AE unless there is a suspicion that the investigational product under study may have interfered with the effectiveness of a contraceptive medication. Pregnancies are followed up to outcome even if the subject was discontinued from the study. Congenital abnormalities/birth defects and spontaneous miscarriages should be reported and handled as SAEs. Elective abortions without complications should not be handled as AEs.

7.3.7. Abnormal Laboratory Findings

An abnormal laboratory finding in absence of any other signs or symptoms is not necessarily an AE. The investigator must review and assess all results provided by the central laboratory throughout the study in a timely manner, and determine whether any abnormal laboratory values are clinically significant (CS) or not clinically significant (NCS), and whether there are associated signs and symptoms. Laboratory abnormalities should be considered clinically significant when they occur after taking study medication, reflect a meaningful change from the screening value(s), and require active management (e.g., abnormalities that require study treatment dose modification, discontinuation, more frequent follow-up assessments, etc.).

Clinically significant laboratory abnormalities will be reported as AEs. If the abnormal laboratory finding is accompanied by signs or symptoms, report the signs and symptoms as the AE in lieu of the abnormal laboratory value. If a diagnosis is available, report the diagnosis.

7.3.8. Hypersensitivity/Anaphylactic Reactions:

Hypersensitivity and anaphylactic reactions will be monitored throughout the study, using the criteria below as defined per Sampson et al. 2006 ([Sampson, 2006](#)).

Anaphylaxis is highly likely when the following criteria is fulfilled:

1. Acute onset of an illness (minutes to several hours) with involvement of the skin, mucosal tissue, or both (e.g., generalized hives, pruritus or flushing, swollen lips-tongue-uvula).

And at least one of the following criteria:

- a. Respiratory compromise (e.g., dyspnea, wheeze-bronchospasm, stridor, reduced PEF, hypoxemia)
 - b. Reduced BP or associated symptoms of end-organ dysfunction (e.g., hypotonia [collapse], syncope, incontinence)
2. Two or more of the following that occur rapidly after exposure to a likely allergen for that patient (minutes to several hours):
 - a. Involvement of the skin-mucosal tissue (e.g., generalized hives, itch-flush, swollen lips-tongue-uvula)
 - b. Respiratory compromise (e.g., dyspnea, wheeze-bronchospasm, stridor, reduced PEF, hypoxemia)
 - c. Reduced BP or associated symptoms (e.g., hypotonia [collapse], syncope, incontinence)
 - d. Persistent gastrointestinal symptoms (e.g., crampy abdominal pain, vomiting)
 3. Reduced BP after exposure to known allergen for that patient (minutes to several hours):

- a. Systolic BP of less than 90 mm Hg or greater than 30% decrease from that person's baseline

7.3.9. Safety Monitoring

Safety will be assessed throughout the study. A medically complete baseline profile of each subject will be established through medical history, a complete physical examination including vital signs and laboratory tests. During the course of the study, vital signs and laboratory tests will be performed at frequent intervals as described in [Appendix 1](#) and [Appendix 2](#). Any medically significant changes from baseline will be monitored throughout the study and appropriate interventions will be taken accordingly. Safety and tolerability will be monitored closely by the Sponsor.

7.3.9.1. Special Reporting Situations

Special Reporting Situations for the IP; pamrevlumab (or placebo) that require safety evaluation include:

- Overdose (any dose greater than 4.1g)
- Suspected abuse/misuse
- Inadvertent or accidental exposure
- Medication error (e.g. incorrect dose administered)
- Drug-drug interactions

Report special situations to the Sponsor's Safety department or delegate within 24 hours of the investigator's knowledge of the event. See SAE Reporting Instructions for more detail.

7.3.9.2. Data Monitoring Committee (DMC)

A Data Monitoring Committee (DMC) will be utilized and will be composed of external experts. Composition and responsibilities of the DMC will be defined in a separate DMC charter. The DMC responsibilities will include review of the safety data in addition to the routine Sponsor pharmacovigilance activities.

8. STATISTICS

8.1. Sample Size Determination

This study is planned to enroll approximately 92 subjects with a 1:1 randomization ratio of assigning to pamrevlumab and placebo, respectively. With PUL version 2.0, the sample size of approximately 92 subjects is needed to detect a treatment difference of 2.0 between treatment arms in change from baseline in the total score of PUL at Week 52, assuming a standard deviation of 2.9 with a 90% power, based on a two-sided two-sample t-test at the alpha level of 0.05.

8.2. Analysis Populations

8.2.1. Intent to Treat (ITT) Population

The ITT population is defined as all randomized subjects regardless of study treatment received. Subjects will be analyzed according to the treatment as randomized. The primary analysis of efficacy will be based on the ITT population.

8.2.2. Safety Population

The safety population is defined as all subjects who have received the study medication. Safety data will be summarized based on the Safety population. Subjects will be analyzed according to the treatment as received.

8.3. Statistical Analysis

8.3.1. General Considerations

The primary efficacy endpoint will be tested at the significance level of 0.05. Upon observing a significant treatment difference in the primary endpoint, the secondary endpoints will be tested taking into consideration the adjustment for the family-wise error-rate of 0.05. The fixed sequence testing procedure will be used for testing of the secondary endpoints in the order listed in [Section 3.2.2](#). The secondary endpoints will be tested sequentially at the 0.05 significance level; once an endpoint pass the 0.05 significance test level then the testing will move to the next secondary endpoint.

Efficacy and safety analyses for treatment comparisons will be based on data observed during the main study. Data from the OLE period will be summarized descriptively.

Baseline characteristics, safety, efficacy and other data will be summarized by treatment arm based on available data in the ITT/Safety Population, except for the parameters specifically indicated otherwise.

Descriptive statistics for continuous variables include: n, mean, standard deviation or standard error, median, minimum, and maximum. Categorical variables will be presented by frequency counts of subjects and percentage. Two-sided 95% confidence intervals will be included for the key efficacy parameters.

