3.1.1.2. Secondary Endpoints

- Change in percent predicted forced vital capacity (ppFVC) from baseline to Week 52, assessed by spirometry.
- Change in the Grip strength of the hands from baseline to Week 52, assessed by Hand Held Myometry (HHM).
- Change in Left Ventricular Ejection Fraction percentage (LVEF %) from baseline to Week 52, assessed by MRI.
- Change in percent predicted peak expiratory flow (ppPEF) from baseline to Week 52, assessed by spirometry.

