8.3.4.2. Analyses of Secondary Endpoints

Changes in ppFVC and ppPEF from Baseline to Week 52

The Change from baseline to Week 52 in ppFVC will be analyzed using a random coefficient model with treatment, visit, visit-by-treatment interaction, and baseline ppFVC as fixed effects; the intercept and linear slope of visit as random effects. The analysis will be based on observed data from subjects in the ITT population.

The Change from baseline to Week 52 in ppPEF will be analyzed using a random coefficient model with treatment, visit, visit-by-treatment interaction, and baseline ppPEF as fixed effects; the intercept and linear slope of visit as random effects. The analysis will be based on observed data from subjects in the ITT population.

Change in the Grip Strength of the Hands from baseline to Week 52, assessed by Hand Held Myometry (HHM)

The Change from baseline to Week 52 in grip strength of the hands will be analyzed using a random coefficient model with treatment, visit, visit-by-treatment interaction, and baseline value as fixed effects; the intercept and linear slope of visit as random effects. The analysis will be based on observed data from subjects in the ITT population.

Change in Left Ventricular Ejection Fraction percentage (LVEF %) from Baseline to Week 52, Assessed by MRI.

Summary of Listing and the analyses of the change from baseline to week 52 in LVEF (%) assessed by MRI will be conducted in the ITT population.

The change from baseline to Week 52 in left ventricular ejection fraction percentage (LVEF%), as assessed by MRI will be analyzed using a random coefficient model with treatment, visit, visit-by-treatment interaction, and baseline value as fixed effects; the intercept and linear slope of visit as random effects.

As an exploratory endpoint, the dichotomous responder (proportion of patients with change from baseline in LVEF% ≥ 0 at Week 52) will be summarized and analyzed. The logistic regression model will be used to compare the proportion of subjects with change from baseline in LVEF% ≥ 0 . The model will include treatment and baseline LVEF%.

For other secondary endpoints, MMRM model will be used in continuous variables; logistic regression model in binary variables; Cox regression model in time-to-event variables. The analysis models will include appropriate baseline factors. Other methods will be applied as appropriate.

Detailed analyses of all secondary endpoints will be clearly outlined in the SAP.

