### 6.6. Efficacy Analyses

The primary and secondary endpoints will be tested using a fixed sequence procedure to preserve the study-wide error rate of 5%. Under the sequential analysis, the primary and secondary efficacy endpoints will be tested in a predefined sequence according to the order listed in Table 1 each at the usual alpha= 0.05 level of statistical significance. The testing will cease when a failure occurs in the pre-determined sequential hypothesis testing and all p-values for the subsequent testing will be considered nominal.

All analyses for efficacy endpoints will be performed for the mITT during the On-Study period (Section 5.3.1.1), unless noted otherwise. Sensitivity analysis on ITT will also be performed on primary and secondary endpoints as supportive evidence.

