**Table 1: Testing Sequence of Primary and Secondary Endpoints**

Testing Sequence	Endpoint
1 (primary endpoint)	Change in the total score of Performance of Upper Limb [(PUL) version 2.0], from baseline to Week 52.
2	Change in percent predicted Forced Vital Capacity (ppFVC) from baseline to Week 52, assessed by spirometry.
3	Change in the total score of Mid-level of PUL from baseline to Week 52
4	Change in the grip strength of the hands from baseline to Week 52, assessed by Hand-Held Myometry (HHM).
5	Change in Left Ventricular Ejection Fraction percentage (LVEF %) from baseline to Week 52, assessed by MRI.

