#### **6.6.3.4. Change in percent predicted peak expiratory flow (ppPEF) from baseline to Week 52, assessed by spirometry**

The change from baseline to Week 52 in ppPEF between two treatment arms will be summarized by analysis visit and analyzed using the RCM model as described above.

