- Expert guidance from key opinion leaders for PUL 2.0 [REDACTED] strongly support the approach of removal of patients with PUL 2.0 entry scores of 1 because these patients do not demonstrate significant decline over a 1-year period and therefore impact meaningful opportunity to demonstrate efficacy.

- Based on changes in the external environment for DMD studies, the Sponsor conducted an analysis of current trials from clinicaltrials.gov and concluded that other clinical trials in the non-ambulatory DMD patient population using the PUL 2.0 as a primary endpoint measure have excluded patients with a PUL 2.0 entry score of 1 at baseline. For example, Capricor Inc./NCT05126758 A Phase 3, Randomized, Double-Blind, Placebo-Controlled Trial Evaluating the Efficacy and Safety of Human Allogeneic Cardiosphere-Derived Cells for the Treatment of Duchenne Muscular Dystrophy A Study of CAP-1002 in Ambulatory and Non-Ambulatory Patients with Duchenne Muscular Dystrophy (HOPE-3).
- Non-ambulatory DMD patients have limited treatment options and have been excluded from clinical trials in emerging treatment classes. Modification of the analysis will result in benefit to non-ambulatory patients as well as increased treatment options.
- The Sponsor has determined that removal of patients with a baseline PUL 2.0 entry score of 1.0 will result in approximately 15 patients removed from the ITT population. The sample size and power calculations are based on the assumptions described in the protocol, and with 15 fewer subjects out of 97 dosed subjects, the trial will have 87% power with 82 subjects in the mITT population.
- Sample size calculation was updated per the latest literature publications and study enrollment. The testing sequence of secondary endpoints was changed from the protocol.
- Changed the analysis method for subscores of regional dimensions (High-level (Shoulder), Distal-level (Wrist and Hand)) of PUL from MMRM to RCM, the same one used in the primary analysis.
- The analysis methods for change from baseline at week 52 in LVEF, Fibrosis Score of the Biceps Brachii, Cardiac Fibrosis Score, Myocardial Circumferential Strain [Global Circumferential Strain (GCS)%] percentage are changed from MMRM to ANCOVA respectively, because there are only two assessments performed during the study for these exploratory endpoints – one at baseline and the other at week 52 and it is not suitable for mixed models of repeated measures.

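### The SAP moves ppPEF from last place in the protocol's fixed testing sequence to exploratory status without naming or justifying the move; restoring it as a final step 6 costs the other tests nothing

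*Protocol*

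**What the plan says.** **Protocol, Amendment 6.** Section 3.1.1.2 lists four secondary endpoints: ppFVC, grip strength, LVEF% and, last, "Change in percent predicted peak expiratory flow (ppPEF) from baseline to Week 52, assessed by spirometry". Section 8.3.1 sets the multiplicity rule: "The fixed sequence testing procedure will be used for testing of the secondary endpoints in the order listed in" a section it gives as 3.2.2, and "The secondary endpoints will be tested sequentially at the 0.05 significance level", with a family-wise rate of 0.05. Section 8.3.4.2 gives the analysis: "The Change from baseline to Week 52 in ppPEF will be analyzed using a random coefficient model", with baseline ppPEF as a fixed effect, in the ITT population.

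**SAP, version 1.0.** Section 6.6 keeps the same kind of procedure: "The primary and secondary endpoints will be tested using a fixed sequence procedure to preserve the study-wide error rate of 5" per cent, in the order of Table 1. Table 1 has five steps: PUL total, ppFVC, Mid-level PUL, grip strength and, last, "Change in Left Ventricular Ejection Fraction percentage (LVEF %) from baseline to Week 52, assessed by MRI". ppPEF is in neither Section 4.2 nor Table 1. It appears among the exploratory endpoints in 4.4, and 6.6.3.4 says "The change from baseline to Week 52 in ppPEF between two treatment arms will be summarized by analysis visit" and analysed with the RCM described earlier. On the order of testing, Section 7 says only "The testing sequence of secondary endpoints was changed from the protocol".

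**The concern.** The SAP presents itself as an elaboration of Amendment 6, and its Section 7 exists to record departures. That section itemises the mITT set, the changes of method, the added composites and the added Mid-level PUL endpoint. The one endpoint removed from the secondary list is not mentioned. A reader of Section 7 alone would know that the order had changed, but not that a protocol secondary endpoint had left the sequence, nor why.

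At stake is whether ppPEF can be claimed. As an exploratory endpoint it has no place in the error-controlled family, so even if all five steps of Table 1 succeed, a ppPEF result is descriptive. The analysis set and the covariate that the protocol fixed for ppPEF also become unclear.

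**Working it through.** **1. The two documents side by side**

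| Item | Protocol | SAP |
|---|---|---|
| Status of ppPEF | Fourth of four secondary endpoints (3.1.1.2) | Exploratory (4.4) |
| Place in the sequence | Last, at 0.05 (8.3.1) | None; Table 1 ends with LVEF% at step 5 |
| Model | RCM (8.3.4.2) | RCM, by reference to earlier text (6.6.3.4) |
| Baseline covariate | Baseline ppPEF | Not stated; the RCM set out in 6.6.1.1.5 uses PUL entry score |
| Population | ITT | Not stated; the 6.6 default is mITT |
| ITT sensitivity analysis | Not needed | ppPEF is not in the 6.6.2.5 list |
| Reason for the move | – | None given in Section 7 |

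**2. The plan's own figure.** The only power statement concerns PUL: difference 2.0, SD 2.9, two-sided 0.05, 1:1. The noncentrality is 2.0 / (2.9 × √(2/n)) with n per arm. For n = 46 it is 3.31, and the exact t-test power is 90.5%, against the stated 90% with 92 subjects. For n = 41 it is 3.12 and the power is 87.0%, against the 87% stated in SAP Section 7 for 82 subjects. Both figures reproduce. Neither says anything about ppPEF, for which the documents give no power.

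**3. Error rate with ppPEF as step 6.** Let k be the first step in the sequence whose null hypothesis is true. Any false claim requires rejection at step k, and that has probability at most 0.05, whatever the number of steps or the correlation. Steps 1 to 5 are tested before step 6 and do not depend on it, so their alpha and power change by exactly 0.

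Simulation (1,000,000 trials, common correlation 0, 0.3 and 0.6) agrees:
- With all endpoints null, the family-wise error is 0.0502, 0.0501 and 0.0498, identical with five and with six steps.
- With very large effects on steps 1 to 5 and ppPEF null, the least favourable case for the added step, it is 0.0500, 0.0498 and 0.0499 with six steps.

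**4. What the added step can deliver.** ppPEF is claimable only if steps 1 to 5 all succeed and step 6 does too. If every step has the same power p and the endpoints are independent, the probability is p⁶. The values of p and of the correlation are assumptions.

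| Assumed power per step | Correlation 0 | Correlation 0.3 | Correlation 0.6 |
|---|---|---|---|
| 50% | 0.5⁶ = 0.016 | 0.081 | 0.179 |
| 80% | 0.8⁶ = 0.262 | 0.395 | 0.521 |
| 90% | 0.9⁶ = 0.531 | 0.620 | 0.710 |

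With ppPEF exploratory, the probability of an error-controlled ppPEF claim is 0 in every cell.

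**The case against.** The strongest reply is that the practical loss is small. ppPEF was already last in the protocol, and as step 6 it would wait for five successes. Respiratory function also keeps an error-controlled test: ppFVC is step 2, and Protocol 2.6.3 regards FVC as the best overall measure of the respiratory muscles. Revising secondary endpoints while blinded is legitimate. All of this stands, and it limits the weight of the point. It does not supply the missing record or reason, and it is no argument against a final step that takes nothing from the others.

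Three stronger readings are tempting, and the documents do not support them.

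- **That the change is hidden.** Section 7 does say that the sequence changed, and 4.4 lists ppPEF openly as exploratory. What is missing is the name of the endpoint and a justification.
- **That the ITT analysis of ppPEF has been abandoned.** This is one reading of a silence. Section 7 ties mITT to the primary and secondary endpoints, and the other exploratory sections, including the neighbouring one on ppFEV1, specify ITT. A dropped line is at least as plausible. What can be said is that no population is stated and that the literal default is mITT.
- **That the move was selective.** Nothing shows that anyone had seen treatment-level ppPEF data. SAP 5.4 plans no interim analysis for efficacy or futility, and Protocol 8.4 requires the SAP to be final before database lock and unblinding.

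**Conclusion.** The point holds as an unexplained reclassification that also leaves the ppPEF analysis underspecified. One of the four protocol secondary endpoints loses the possibility of an error-controlled claim, Section 7 neither names nor justifies this, and the population and covariate are left to inference.

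Restoring ppPEF as the final step is free for the rest of the sequence: steps 1 to 5 are unaffected, and the Table 1 family stays at or below 5%. That result needs no assumption about correlation, only valid tests at each step. The benefit is conditional, at roughly 0.02 to 0.71 under the assumed powers and correlations.

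A reader might infer that the six-step sequence would control error over every secondary endpoint. It would not. The three composite z-scores are secondary in SAP 4.2, but they sit outside Table 1 with their own one-sided 0.025 criterion (6.6.2.4.3), and the error result here does not cover them. Nor does the pointer in Protocol 8.3.1 to Section 3.2.2, which is the placebo section, put the testing order in doubt: the intended list is plainly 3.1.1.2, and the slip is clerical.

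**What to change.** By SAP amendment, before unblinding:

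1. Restore ppPEF to Section 4.2 and add it to Table 1 as step 6, after LVEF%, at 0.05.
2. Move 6.6.3.4 into the secondary RCM section (6.6.2.1), but write out the covariate as baseline ppPEF, as in Protocol 8.3.4.2. A bare reference to 6.6.1.1.5 would bring in PUL entry score instead.
3. State the analysis population and add ppPEF to the ITT list in 6.6.2.5. Without this, moving it into 6.6.2.1 would give an mITT test only, and not the ITT analysis that the protocol specified.
4. Record the restored endpoint and the final order in Section 7.

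If the sponsor has a reason to keep ppPEF exploratory, naming the move and giving that reason in Section 7, with items 2 and 3 still specified, would cure the documentation gap but not the lost claim.

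The cost is SAP wording: the spirometry is already collected, an RCM for ppPEF is already planned, and no other test changes. Correcting the cross-reference in Protocol 8.3.1 to 3.1.1.2 is a separate clerical protocol change.
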